6.5 Post-Intervention (between weeks 20-26)

Participants in both arms are asked to complete a post-intervention assessment (between weeks 20-26), which includes:

Post-intervention online questionnaire: Similar items are included on the post-intervention questionnaire as with the baseline and interim assessment with the exception that participants and their caregivers, if applicable, are asked to rate the intervention on multiple dimensions.

- Benefits of PA⁵⁰ (participant)

- Subjective Norms survey⁵¹ (participant & caregiver, if applicable)

- Social Support for Exercise survey⁵² (participant)

Barriers to Exercise survey⁵³ (participant)
Self-Efficacy for Exercise Scale⁵⁴ (participant)
Patient-Reported Outcomes Measurement Information System⁴⁵⁻⁴⁷ (participant & caregiver, if applicable)
International Physical Activity Questionnaire^{48,49} (participant & caregiver, if applicable)
Cardiac Anxiety Questionnaire⁵⁵ (participant)
Family Environment Scale⁵⁸ (caregiver, if applicable)
Child Vulnerability Scale⁵⁷ (caregiver, if applicable)
Changes in Health (participant)
Post-Intervention Satisfaction (participant & caregiver, if applicable)

MVPA and SB: Participants wear an accelerometer again for the same measurement period (7 days) as in previous assessments and complete self-monitoring PA logs in the case they cannot wear the accelerometer (e.g. swimming).

VO_{2max}: VO₂ measurement is obtained again with a graded exercise stress test using a modified Bruce protocol. Participants who were found to have an arrhythmia or show evidence of cardiac ischemia during exercise stress testing will be immediately referred to their cardiologist for follow-up.

Compensation: Caregivers are compensated \$20 during the exercise stress test visit after they complete the post-intervention surveys. Participants are compensated \$100 for completion of the post-intervention survey, exercise stress test, and returning the accelerometer with at least 4 days (1 weekend day, 3 weekdays), for at least 10 hours per day of data. Additionally, participants parking and mileage to/from the hospital for the exercise stress test are reimbursed.

6.6 Focus Groups (after post-intervention assessment)

Participants in the intervention arm are asked to partake in a focus group lasting approximately 1.5 hours, to discuss their experiences in the study. There will be 3-4 groups that meet via videoconferencing with 6-8 participants per group.

Compensation: Participants are compensated \$50 for being in the focus group.

6.7 6-Month Follow-up (between weeks 46-50)

Participants in both arms are asked to complete a 6-month follow-up assessment (between weeks 46-50), which includes:

6-month follow-up online questionnaire: Participants are asked to complete the same questionnaire that was completed at the interim assessment.

- Benefits of PA⁵⁰

- Subjective Norms survey⁵¹

- Social Support for Exercise survey⁵²

- Barriers to Exercise survey⁵³

- Self-Efficacy for Exercise Scale⁵⁴

- Patient-Reported Outcomes Measurement Information System⁴⁵⁻⁴⁷

- International Physical Activity Questionnaire^{48,49}

- Cardiac Anxiety Questionnaire⁵⁵

- Changes in Health

MVPA and SB: Participants wear an accelerometer again for the same measurement period (7 days) as in previous assessments and complete self-monitoring PA logs in the case they cannot wear the accelerometer (e.g. swimming).

Compensation: Participants are compensated \$75 for completion of the 6-month follow-up assessment survey and wearing the accelerometer for at least 4 days (1 weekend day, 3 weekdays), for at least 10 hours per day.

6.8 Additional Incentive

In addition to the compensation described in sections 6.2, 6.4, and 6.5, participants in both arms are able to keep the Fitbit.

7 ASSESSMENT OF SAFETY

7.1 Methods and Timing for Assessing, Recording, and Analyzing Safety Parameters

7.1.1 Adverse Events

Adverse Event

For the current study, an adverse event is an unanticipated change in physical symptoms that is (1) concerning to the participant and (2) results in seeking medical attention. We do not anticipate any severe medical adverse events due to study procedures. However, medical events that occur for participants during the course of the study are comprehensively documented, including events during the stress test, symptoms reported during the course of the intervention, dates and reasons for pauses in the study protocol due to symptom reporting, and determination of ability to proceed by participants' cardiologists. All unscheduled cardiology outpatient visits, visits to urgent care or the emergency department, unscheduled hospitalizations, or any other changes in health are documented. Both participants in the comparison and intervention arms are asked whether they sought medical attention in the aforementioned contexts during the interim and post-intervention questionnaires.

The current study has several procedures in place to reduce the likelihood of serious adverse events. Potential participants' cardiologists are notified prior to being recruited for the study and excluded if the cardiologist has communicated or documented any concerns about that adolescent engaging in MVPA. All participants undergo a baseline exercise stress test and are not approached for recruitment for Phase 2 if contraindications are detected in Phase 1. In the rare event that a participant has an acute medical event during the exercise stress test, appropriate hospital procedures are enacted, which include calling an emergency response team and immediate evaluation by a cardiologist. The same procedures used for patients undergoing exercise stress testing as part of a medical evaluation are initiated and followed. During the course of the intervention, if an adolescent reports cardiac symptoms that are concerning to the participant and are new since the last cardiac evaluation, PA coaches are trained to request that the adolescent tell his/her caregiver (if they haven't already done so) and contact their cardiologist. Adolescents and their caregiver have given the study PI, [name], permission to talk with the cardiologist in the

instance that a concerning and/or new cardiac symptom is reported. All study procedures are put on hold until the adolescent is evaluated by the cardiologist and cleared to proceed with the study.

7.1.2 Procedures to be Followed in the Event of Abnormal Test Values or Abnormal Clinical Findings

Incidental findings from the exercise stress test are communicated to the participant and caregiver, if applicable, and the participant's cardiologist. The cardiologist will make a determination as to whether the participant may proceed with the study if an abnormal event, or incidental finding, is detected.

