2.3 Potential Risks and Benefits

2.3.1 Potential Risks

The current research study complies with the federal regulations definition of “minimal risk” [§45 CFR 46.102(i)] “that the probability and magnitude of harm or discomfort anticipated in the research are not greater, in and of themselves, than those ordinarily encountered in daily life or during the performance of routine physical or psychological examinations or tests.” Consequently, the CHD-PAL Study was reviewed by the NCH Institutional Review Board under §45 CFR 46.404 “Research not involving greater than minimal risk.”

Exercise training has been established as safe for most CHD survivors and PA promotion in this population is highly recommended. Nevertheless, we have designed a protocol that implements several safeguards to reduce potential risk. Before a potential participant is approached for recruitment, his/her cardiologist is contacted to determine if the adolescent is able to safely engage in MVPA. After receiving the cardiologist’s approval and the CHD survivors is recruited, then he/she undergoes an exercise stress test to rule out the presence of arrhythmia or cardiac ischemia, which would preclude them from engaging in regular MVPA, and therefore exclude them from participating in Phase 2 of the study. Exercise stress tests are conducted within the same space used for outpatient cardiology clinic and are staffed by at least one cardiologist. As part of the exercise stress test protocol, participants are encouraged to reach the limitations of their physical capacity, which can be uncomfortable. Thus, participants are told that they may experience normal levels of physical discomfort when undergoing the exercise stress test. Upon completion of the test, participants are provided with a towel and water, and are monitored by clinical staff throughout the duration and recovery of the test. If the exercise stress test results demonstrate arrhythmia or cardiac ischemia both the participant and the participants’ primary cardiologist are notified. Although learning this information could be distressing to participants or their caregivers, identification of an abnormality would have potential benefits to participants as well.

Similar to the exercise stress test, participants in the intervention arm may experience uncomfortable physical sensations due to exercising, including sore muscles, fatigue, and shortness of breath. If the participant has new cardiac-related symptoms since his/her last

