cardiology check-up that are concerning to the participant and caregiver, the interventionist (i.e. PA coaches) will recommend contacting the participant's cardiologist and the study procedures are put on hold until the cardiologist clears the participant to return to the study. The interventionist also contacts the study PI, [name], who notifies the participant's cardiologist that the participant is experiencing symptoms.

During videoconferencing, PA coaches conduct sessions in privacy and encourage participants to do the same. The same will be encouraged for those who participate in the focus groups. Coaches undergo the same training as other research staff at NCH, including completing Collaborative Institutional Training Initiative (CITI) certification and a day-long instructional seminar on protecting human subjects. Videoconferencing has a lower risk of privacy breach than email communications.

Participants are informed that participation is voluntary and that they have the right to withdraw from the study at any time, as well as may refuse to answer or may skip any question(s) that cause discomfort. While not anticipated, participants could experience some discomfort when completing survey items about their heart condition or treatment history. However, this risk is very small. If discomfort occurs, it would likely be transient and minimal. Participants are encouraged to discuss any concerns about the content of the survey items with study personnel, who have experience using these questionnaires and are trained to respond appropriately. The more likely risk to participants is boredom while completing the questionnaires.

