7.2 Reporting Procedures

7.2.1 Adverse Events

Any adverse events are reported to the DSMB and IRB.

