7.4 Halting Rules

If it is found that the study intervention is related to any serious adverse events, enrollment will be temporarily suspended until a safety review is convened. The DSMB will decide whether the study should continue per protocol, proceed with caution, be further investigated, be discontinued, or be modified and then proceed. Suspension of enrollment (for a particular group or for the entire study) is another potential outcome of a safety review.

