7.5 Safety Oversight

Safety oversight of this study is under the direction of the study PI, NCH IRB, as well as a DSMB. The DSMB consists of two faculty members from NCH. [name] [name] is a dual-boarded pediatric and adult congenital cardiologist housed in the Heart Center at NCH. [name] is a board-certified pediatrician and a former Director of the Division of Epidemiology,

Statistics, and Prevention Research at the National Institute of Child Health and Human Development. [name] has been involved as a Co-I of multiple RCTs and currently serves on the DSMB for an NIH-funded clinical trial. The NCH IRB has reviewed and approved the Data and Safety Monitoring Plan for this study. Bi-yearly reports summarizing the number of participants enrolled, the number of stress tests completed, the number of abnormalities detected during exercise stress testing, and the number of participants who have contacted their cardiologists due to concern over symptoms while engaged in the treatment arm will be provided to the DSMB. This summary is submitted to the IRB with the annual review.

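### The adverse event definition in section 7.1.1 can exclude some serious events from DSMB reporting, the halting rule relies on an undefined term, and one entry condition (care-seeking) is prompted in one arm only

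*Combined protocol and SAP*

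**What the plan says.** Section 7.1.1 of the protocol states that "an adverse event is an unanticipated change in physical symptoms that is (1) concerning to the participant and (2) results in seeking medical attention". The same section records far more than this: "All unscheduled cardiology outpatient visits, visits to urgent care or the emergency department, unscheduled hospitalizations, or any other changes in health are documented". It adds that both arms are asked at the interim and post-intervention questionnaires whether they sought medical care.

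The reporting rule in section 7.2.1 is one sentence: "Any adverse events are reported to the DSMB and IRB". Section 7.4 sets the halting rule: "If it is found that the study intervention is related to any serious adverse events, enrollment will be temporarily suspended", pending a safety review.

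Section 7.5 lists what the bi-yearly DSMB summary contains: participants enrolled, stress tests completed, "the number of abnormalities detected during exercise stress testing", and treatment-arm participants who contacted their cardiologist over symptoms.

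Two parts of section 2.3.1 bear on how the definition works in each arm. Intervention participants may feel "uncomfortable physical sensations due to exercising, including sore muscles, fatigue, and shortness of breath". If a participant has new and concerning cardiac symptoms, "the interventionist (i.e. PA coaches) will recommend contacting" the cardiologist.

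**The concern.** The definition decides what is reported event by event, and the halting rule builds on it. Its conditions describe how the participant experienced and reacted to a symptom, not how grave the event was. An event can therefore be serious, be documented, and still fail the definition. The participants have moderate to complex congenital heart disease, many are minors, and they are asked to exercise more, so the events most likely to be missed are ones the DSMB would want to see.

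Care-seeking is also an entry condition, and only the intervention arm has a coach whose task includes prompting it. The DSMB could be shown an arm difference that reflects coaching, not harm, or could fail to see a real one.

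**Working it through.** The documents give no safety rate to reproduce, so the main check sets the sections side by side.

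**Step 1. Apply the definition literally.** It has four parts: unanticipated, a change in physical symptoms, concerning to the participant, and care sought.

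| Event | Condition that fails | Adverse event under 7.1.1? | Other stated route to the DSMB |
|---|---|---|---|
| Hospitalization for an unexpected, concerning symptom | None | Yes | Not needed; 7.2.1 applies |
| Silent arrhythmia or ischemia at the post-intervention stress test | No change in symptoms; found by a study test | No | Bi-yearly count of abnormalities (7.5) |
| Sudden death | Participant concern and care-seeking cannot be shown | No | None stated |
| Emergency visit for breathlessness or fatigue, intervention arm | Possibly unanticipated, given 2.3.1 | Depends on the reading | None stated for emergency visits |
| New symptom reported to a coach, study paused, participant never evaluated | Care not sought | No | None stated |

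**Step 2. Trace what depends on it.** Section 7.2.1 names adverse events only. Section 7.3 takes cardiac-related adverse events to the cardiology team. Section 7.4 uses serious adverse events, which no section defines. No section says how a documented event that fails the definition reaches the DSMB.

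**Step 3. See whether the bi-yearly summary closes the gap.** Of its four items, two concern safety findings. Hospitalizations, emergency visits and deaths are not listed. Cardiologist contacts are counted for the treatment arm only.

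**Step 4. Compare the arms.** The intervention arm has 8 coach sessions over 20 weeks (section 5.4). The comparison arm has no coach and is not contacted about the Fitbit again (section 5.7). The questionnaires do not restore balance: as section 7.1.1 describes them, they ask about care sought, so a symptom without care-seeking stays uncounted. Section 6.4 also describes the interim health-change questions as an exception for the comparison arm, which does not fit section 7.1.1.

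**Step 5. Illustrate the size.** Only the arm size, n = 50 (section 5), comes from the documents. The rest is assumed: symptom risk s = 0.10 to 0.30, equal in both arms; care-seeking c0 = 0.30 to 0.50 unprompted and c1 = 0.70 to 0.90 when coached. Expected counted events = n × s × c.

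- Comparison arm: 50 × 0.10 × 0.30 = 1.5, up to 50 × 0.30 × 0.50 = 7.5.
- Coached arm: 50 × 0.10 × 0.70 = 3.5, up to 50 × 0.30 × 0.90 = 13.5.
- Ratio c1/c0: 0.70/0.50 = 1.4, up to 0.90/0.30 = 3.0, with no true difference.
- If prompting has no effect, c1 = c0 and the ratio is 1.0.
- If a share a = 0.25 to 0.50 of symptoms is classed as anticipated in the coached arm only, the ratio is (1 − a) × c1/c0: from 0.50 × 0.70/0.50 = 0.7 to 0.75 × 0.90/0.30 = 2.25.

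**The case against.** The strongest defense is that the ordinary serious event is covered: an unexpected, concerning symptom that leads to hospitalization meets every condition and is reported. This stands. A reader might infer that documented serious events never reach the DSMB, and the documents do not support that. Stress-test abnormalities also reach it as counts, and section 7.1.2 sends such findings to the participant and the cardiologist.

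Several other objections narrow the point:

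- Section 2.3.1 lists breathlessness and fatigue as exercise sensations and then treats new cardiac symptoms separately. An emergency visit need not be read as anticipated, so that case is arguable.
- A pause lasts until the cardiologist evaluates or clears the participant, and the PI notifies the cardiologist (sections 2.3.1 and 7.1.1). The gap is confined to participants who are never evaluated.
- Sections 5.3.4 and 10.5 let the DSMB end the study without tying its findings to adverse events as defined. Even so, it can act only on what it receives.
- Section 7.5 mentions an approved Data and Safety Monitoring Plan, and section 11.5 a Manual of Procedures. Neither was available, and either might hold a wider reporting rule. The gap is shown for the protocol text only.
- Section 7.9 plans no between-arm comparison of adverse events. A reader might infer that a planned analysis is biased; none is planned. What remains is the effect on counts that the DSMB sees.
- A reader might also infer that the coached arm must show more events. Expected sensations are named for that arm, which could lower its count.

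Cardiologist clearance, the baseline stress test and the symptom-triggered holds lower the risk, but they do not repair the reporting rule.

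**Conclusion.** The point holds as a defect in a stated rule, not as missing detail. Taken literally, the definition leaves out some serious events, with sudden death and silent stress-test findings the clearest cases. Some documented hospitalizations or emergency visits may also be left out if judged anticipated. The halting rule depends on an undefined term, and the bi-yearly summary only partly fills the gap.

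Arm dependence follows from the text. Its size does not: the ratios above rest on assumed symptom and care-seeking rates. An upward shift in the coached arm is likely, not certain.

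This should be fixed. It concerns safety oversight and leaves the primary outcome and its analysis untouched. The conclusion assumes that the unseen monitoring plan and manual do not already set a wider rule.

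**What to change.** 1. In section 7.1.1, define an adverse event as any untoward medical occurrence after consent. Record expectedness, participant concern, care-seeking and relatedness as attributes of the event, not as conditions for counting it.
2. Define a serious adverse event by outcome, so that the term in section 7.4 has a fixed meaning. What section 7.4 does once the term is met need not change.
3. State in sections 7.2.1 and 7.5 that the medical events already documented under section 7.1.1 are reported to the DSMB, for both arms. This includes cardiologist contacts in the comparison arm.
4. Reconcile section 6.4 with section 7.1.1 so that both arms get the same health-change questions, covering symptoms for which no care was sought. List coach-elicited events separately, so that counts from the common questionnaires can be read side by side.

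The cost is an IRB amendment, more events to log and report, recording of the attributes for each event, and possibly one added questionnaire item. If the Data and Safety Monitoring Plan already contains a wider rule, steps 1 to 3 reduce to bringing the protocol into line with it.

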7.2 Reporting Procedures

7.2.1 Adverse Events

Any adverse events are reported to the DSMB and IRB.

7.3 Type and Duration of Follow-up of Subjects after Adverse Events

All cardiac-related adverse events are discussed with the cardiology medical team. The cardiology medical team determines whether participation in the study is suspended, and for how long, or terminated.

7.4 Halting Rules

If it is found that the study intervention is related to any serious adverse events, enrollment will be temporarily suspended until a safety review is convened. The DSMB will decide whether the study should continue per protocol, proceed with caution, be further investigated, be discontinued, or be modified and then proceed. Suspension of enrollment (for a particular group or for the entire study) is another potential outcome of a safety review.

7.5 Safety Oversight

Safety oversight of this study is under the direction of the study PI, NCH IRB, as well as a DSMB. The DSMB consists of two faculty members from NCH. [name] [name] is a dual-boarded pediatric and adult congenital cardiologist housed in the Heart Center at NCH. [name] is a board-certified pediatrician and a former Director of the Division of Epidemiology,

Statistics, and Prevention Research at the National Institute of Child Health and Human Development. [name] has been involved as a Co-I of multiple RCTs and currently serves on the DSMB for an NIH-funded clinical trial. The NCH IRB has reviewed and approved the Data and Safety Monitoring Plan for this study. Bi-yearly reports summarizing the number of participants enrolled, the number of stress tests completed, the number of abnormalities detected during exercise stress testing, and the number of participants who have contacted their cardiologists due to concern over symptoms while engaged in the treatment arm will be provided to the DSMB. This summary is submitted to the IRB with the annual review.

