Description of the Intervention:	Phase 2 of the study consists of being randomized into one of two arms; the comparison arm receives a Fitbit and an exercise prescription based on the results of the Phase 1 stress test. The intervention arm receives a Fitbit, an exercise prescription, and 8 videoconferencing sessions with a PA coach, which takes place over 20 weeks. Each session lasts 20-30 minutes and focuses on changing attitudes, perceptions of social norms, and perceptions of control over for engaging in PA, based on the principles of the Theory of Planner Behavior.
Objectives:	The long-term goal of this research study is to establish an effective intervention for sustaining increased levels of MVPA that will reduce morbidity and healthcare costs for CHD survivors. The objective of this study is to adapt a lifestyle PA intervention to transition-age adolescent and emerging adult CHD survivors at greater risk for future morbidity due to having more complex disease. This will involve (1) assessing feasibility of the intervention to participants based on subjective ratings and objective recruitment and retention information, as well as (2) evaluating preliminary efficacy of the intervention on time spent in MVPA and SB, as well as improvement in cardiorespiratory fitness as assessed by changes in VO_{2max} . We hypothesize that (1) participants will positively rate the intervention on multiple dimensions, including easy to access, enjoyable, and pertinent. Additionally, recruitment and retention rates are predicted to be $\geq 75\%$. We also predict that (2) participants in the intervention arm will (A) increase MVPA (primary outcome), (B) decrease SB (secondary outcome), and (C) demonstrate an increase in VO_{2max} (secondary outcome) at post-intervention relative to those in the comparison arm. The rationale for the proposed research is to obtain pilot data that will shape the next phase of investigation: determining the efficacy of this intervention for sustaining increased PA. Ultimately, we hope that knowledge gained from this line of research will extend longevity and optimize quality of life for CHD survivors as they age into adulthood.
Description of Study Design:	Randomized controlled trial with two treatment arms: (1) Comparison arm: Fitbit, exercise prescription and (2) Intervention arm: Fitbit, exercise prescription, and 8 videoconferencing sessions with a PA coach over the course of 20 weeks.

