4 STUDY DESIGN

This single-site study is a randomized clinical trial of a Fitbit and exercise prescription vs. a Fitbit, exercise prescription, AND videoconferencing sessions with a PA coach over the course of 8 sessions in 20 weeks.

For Phase 1, participants are asked to complete less than 30-45 minutes of questionnaires wear an accelerometer for 7 days, and undergo an exercise stress test. For adolescent participants, a caregiver is asked to complete 20-30 minutes of questionnaires. Once the exercise stress test is completed and the accelerometer is returned, participants are compensated \$100. Once caregivers complete the online questionnaires, they are compensated \$20. Parking and mileage reimbursement to/from the hospital is provided.

If a participant engages in less than 60 minutes of MVPA per day and has no contraindications on the exercise stress test, he/she is approached for participation in Phase 2. Once recruited, participants receive a Fitbit and an explanation of their exercise prescription based on the results of their exercise stress test as provided by an exercise physiologist. Next, study staff open an envelope (pre-prepared by the study statistician, [name]) to reveal the participant's study arm designation.

Participants are randomized to 1 of 2 arms: the comparison arm, which receives a Fitbit and the exercise prescription, or the intervention arm, which also receives a Fitbit and exercise prescription PLUS videoconferencing sessions (e.g., FaceTime, Google Hangouts or Skype) with a PA coach (8 sessions over the course of 20 weeks). Each session lasts approximately 30 minutes and is audiotaped. The intervention arm focuses on changing attitudes (e.g., identifying pleasurable physical activities), perceptions of social norms of PA (e.g., problem-solving ways to receive support from family and friends) and perceptions of control for engaging in PA (e.g., increasing self-efficacy through goal setting and reducing barriers), as outlined by the Theory of Planned Behavior, to increase time spent in MVPA and decrease SB. The Fitbit is used to facilitate goal setting and self-monitoring for participants in the intervention arm.

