7.6 Study Hypotheses

Hypothesis 1: Participants are hypothesized to rate the intervention as not burdensome, easy to access, and appealing. Additionally, recruitment and retention rates are predicted to be $\geq 75\%$.

Hypothesis 2: Participants in the treatment arm will (A) increase MVPA relative to those in the comparison arm at post-intervention, (B) decrease SB relative to those in the comparison arm, and (C) demonstrate an increase in VO_{2max} at post-intervention relative to those in the comparison arm.

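### The periodic DSMB summary counts symptom-driven cardiologist contacts in the intervention arm only, with no by-arm table or denominator, so on its own it cannot separate an excess from background

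*Combined protocol and SAP*

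**What the plan says.** Section 7.5 (Safety Oversight) names four contents of the bi-yearly DSMB report: enrolment, stress tests done, stress-test abnormalities, and "the number of participants who have contacted their cardiologists due to concern over symptoms while engaged in the treatment arm". Only the last concerns symptoms, and it alone is limited to one arm. No item is described as split by arm or given with a denominator.

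The term treatment arm most naturally means the coached arm. Section 7.6 contrasts the two: "Participants in the treatment arm will (A) increase MVPA relative to those in the comparison arm at post-intervention". The Protocol Summary does once describe the trial as a "Randomized controlled trial with two treatment arms", so the wording is not perfectly uniform.

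Four other places bear on the point:

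- Section 4 describes "the comparison arm, which receives a Fitbit and the exercise prescription", so both arms are given an exercise prescription.
- Section 7.1.1 defines an adverse event as an "unanticipated change in physical symptoms that is (1) concerning to the participant and (2) results in seeking medical attention". It says unscheduled care is documented, and that "Both participants in the comparison and intervention arms are asked whether they sought medical attention in the aforementioned contexts" at the interim and post-intervention questionnaires.
- Section 7.2.1 sends any adverse event to the DSMB and IRB, without restriction by arm and without specifying a table.
- Section 7.4 suspends enrolment "If it is found that the study intervention is related to any serious adverse events", and allows a later suspension to apply to one group only.

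**The concern.** Participants have moderate or complex heart disease, so some will call their cardiologist about symptoms whatever arm they are in. A count from one arm mixes that background with any effect of the intervention, and the report gives the board nothing concurrent to set it against. The randomised comparison group would supply that reference, and the protocol already collects information on it.

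Two things are at stake. A count that is only background could look like harm, or a real excess could pass as background. Also, if the shared exercise prescription led to symptom contacts in the comparison arm, the symptom item would not show them.

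**Working it through.** The plan states no figure on this point, so there is none to reproduce. The check is a reading of the text followed by an illustration.

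**Text**

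1. Section 7.5 restricts the symptom item to the treatment arm, and section 7.6 shows that this means the arm opposed to the comparison arm.
2. Section 7.2.1 is a second route to the board and covers both arms. Most symptom-driven cardiologist contacts would meet the section 7.1.1 definition of an adverse event.
3. The two routes need not count the same things. An adverse event must be unanticipated, while section 2.3.1 names fatigue and shortness of breath among the sensations that exercise may bring. A contact about one of these could count under 7.5 in the intervention arm and yet not be an adverse event in either arm.
4. Neither section specifies counts by arm, number at risk or follow-up time.
5. Ascertainment differs by arm. Sections 2.3.1 and 7.1.1 have coaches advise contact with the cardiologist when new, concerning symptoms are reported. The comparison arm has no coach, and under section 5.7 is not contacted again about the Fitbit. Part of the 7.5 count is therefore produced by coaching itself.

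**Illustration (assumed counts and rates)**

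Inputs: 50 per arm (section 5); an assumed 8 contacts among 50 (16%); assumed background rates of 2% to 20%.

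*One arm only.* P(X ≥ 8) = Σ C(50,k) p^k (1−p)^(50−k), for k = 8 to 50:

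| Assumed background p | Expected contacts, 50p | P(X ≥ 8) |
|---|---|---|
| 2% | 1.0 | <0.0001 |
| 5% | 2.5 | 0.003 |
| 10% | 5.0 | 0.12 |
| 15% | 7.5 | 0.48 |
| 20% | 10.0 | 0.81 |

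The same count is extreme at one end of the range and below expectation at the other.

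*With a comparison-arm count, collected in the same way.* Two-sided Fisher exact test. For 8/50 against 0/50, p = 2 × C(50,8)/C(100,8) = 0.006. The other comparisons are computed in the same manner:

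| Comparison arm | p |
|---|---|
| 0/50 | 0.006 |
| 1/50 | 0.031 |
| 2/50 | 0.09 |
| 4/50 | 0.36 |
| 8/50 | 1.0 |

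*Limits of the comparison.* Power of the two-sided 5% Fisher test to show an intervention-arm excess, summed over all pairs of counts at 50 per arm, is about 0.20 for 10% against 20%, and 0.64 for 10% against 30%. The Protocol Summary allows 3 years for enrolment, so earlier reports would have fewer at risk and less power.

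**The case against.** A reader might infer that the board never sees comparison-arm events, or cannot judge harm at all. The documents do not support that. Section 7.2.1 sends adverse events from either arm to the DSMB, and the stress-test abnormality item in 7.5 has no arm restriction, although both arms have a post-intervention stress test (section 6.5).

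A reader might also infer that the halting rule depends on this count. It does not. Section 7.4 is triggered by related serious adverse events and sets no threshold on contacts. Sections 7.1.1 and 7.3 provide for case-by-case review by cardiologists, and the DSMB may ask for further investigation.

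Three more points stand. The trial is a behavioural pilot classed as minimal risk, with prior cardiologist approval and stress-test screening. Raw counts set side by side could create a false excess, because coaches prompt contacts in one arm only. Section 7.5 also mentions an IRB-approved Data and Safety Monitoring Plan; if that is a separate document, it may already call for tables by arm.

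These points narrow the concern and shape the remedy, but they do not remove it. Individual reports without arm totals and denominators do not provide rates, and the one symptom item in the periodic summary still covers a single arm.

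**Conclusion.** The point holds as a gap in the periodic summary. As written, 7.5 gives the board a one-arm symptom count with no concurrent reference and no denominator, and that summary alone cannot separate an intervention-related excess from background. Comparison-arm adverse events remain reportable individually.

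The size cannot be stated as a rate, because the documents give no background figure. Under the assumed range of 2% to 20%, the probability of 8 or more contacts among 50 runs from below 0.0001 to 0.81. Adding the other arm would make the item easier to interpret, but with low power to settle the question.

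This rests on reading treatment arm as the intervention arm, as 7.6 supports, and on no by-arm table being specified in a monitoring plan outside these documents. It is a modest amendment worth making.

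**What to change.** Amend section 7.5 so that each bi-yearly report gives, for each arm, symptom-driven cardiologist contacts and unscheduled care, with number at risk and follow-up time. Supply the table to the DSMB in closed form if the study team should not see arm totals.

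Take the between-arm counts from a source common to both arms: the questionnaire items on medical attention described in 7.1.1, or medical records. If the questionnaire is used, first reconcile 7.1.1 with section 6.4. The wording of 6.4 can be read as giving the interim health-change questions to the comparison arm only, whereas 7.1.1 says both arms are asked.

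Show coach-prompted contacts and protocol pauses separately, not as part of the between-arm comparison. State in the report that small numbers limit what the comparison can show.

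The cost is small: someone must tabulate by arm and access must be restricted. Section 7.1.1 already provides for collecting the underlying information. No clinical rule changes.
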